**Title: Effect of Sport Education in University Required PE on Students'
Perceived Physical Literacy and Physical Activity Level**

NCT number: NCT03888885

Date: 12/9/2021

Study Protocol

Research design

This study employed a 10-lesson cluster-randomized study design to examine the effect of sport education on domains of student PL and physical activity levels. Questionnaires, accelerometers, and video recordings of PE lessons were used to collect self-report and objective data measures.

[figure not shown]
Eligibility and randomization

Only one university in Hong Kong fully funded by the University Grants Committee and requires the completion of two semesters of PE coursework for graduation. Lecturers in the PE program are required to have a master's degree or above and have more than 5 years of teaching experience. All lecturers attended a 12-h continuous professional development workshop on sport education. Of the 25 lecturers who attended the workshop, 11 of them consented to participate in the study. The required sample size of students was calculated based on the hypothesized effect sizes and the likely rates of participants dropout for outcome measures. A total number of 2886 students were admitted to the university in the academic year, with an estimated required cluster sample size of 341 with an effect size of 0.25, α of 0.05, and a power of 0.95 (Faul et al. 2007). In anticipation of 10–20% of the dropout rate across data collection phases, this led to a required number of 8 classes for each of the sport education and traditional groups. PE classes were initially grouped by lecturers and types of sports (individual sports, team sports, and physical conditioning) and then randomly assigned to each intervention (Fig. 1) by a computer-generated sequence (GraphPad Software, Inc.) conducted by a statistician who was blind to the purposes of the study. The demographic background and corresponding courses for each of the eight lecturers are shown in Table 1. Students were eligible to participate in the study if they were aged 18 or above and indicated all negative statements in the self-screening Physical Activity Readiness Questionnaire (Thomas et al. 1992) which can uncover heart, circulatory, balance, medication, emotional, and joint problems that could make exercise difficult or dangerous for some people. Written consent for study participation was also obtained.

PE curriculum intervention

The goals of the required PE courses are to encourage students to participate in lifelong physical activities by developing their skills and fitness, motivation, knowledge, social, and sportsmanship. These domains of learning connect to the holistic attributes of PL; however, this term is not explicitly mentioned in course objectives or used to design curricular materials. PE teachers in Hong Kong generally adopt a teacher-directed approach in delivering content and accomplishing the objective of the curriculum (Ha 2016). The implementation of sport education was an attempt to infuse a more student-centered instructional model that has been empirically validated to elicit positive changes in student PL (Farias et al. 2020). The sport education professional development workshop focused on the development of a season structure, the changing roles of teachers and students, the assessment of personal and social responsibility, and the application of related pedagogical methods. Following the instructor workshop, two meetings were held with the PE lecturers to discuss the design of specific coursework and class materials. Sport education seasons were designed for badminton, basketball, handball, physical conditioning, swimming, woodball, and volleyball. Each sport education season included ten 90-min lessons, 1-day per week with each season following the five-phase sequence of team

Figure 3.1. Participant Flow of Enrolment and Allocation in the Trial.

selection, teacher-directed, preseason, formal competition, and a culminating event (Hastie et al. 2014). Participants in each class were divided into teams for the duration of each season and assigned specific sport-related roles (e.g., coach, fitness trainer, equipment manager) at the end of the team selection phase. Students gradually increased their responsibility for learning and had equal opportunity to participate in every lesson with tasks progressing from drills to modified games and competitions to obtain more authentic sports experiences within the lessons. To evaluate model fidelity, a sample lesson from each phase of the sport education season was observed and coded by the primary researcher using the sport education benchmark observational instrument (Ko et al. 2006; Sinehnikov 2009). Fidelity analysis revealed 100% compliance with season, affiliation, formal competition, and culminating event benchmarks.

Participants within the control group classes attended PE classes where teachers used traditional teacher-directed methods to teach the specific activities. These lessons started with a teacher-directed warm-up routine, followed by direct instruction of skills practices, and games without a consistent team and modification to meet the objective of the courses. Within the direct teaching approach, the teacher was assigned responsibility for all task presentation components of the learning tasks. No student role responsibilities or student-directed tasks were included within this approach. Students within the intact class changed teams each lesson and scores were not formally recorded for the game outcomes. Analysis with the sport education benchmark observational instrument revealed none of the instructional behaviors associated with the key features of the model.

Data collection protocol

During the first week of the semester, a baseline questionnaire was distributed by the researchers and lecturers to all participants to obtain students' self-reported information including perceived PL, physical activity levels, and perceptions of motivational climate in PE classes. Demographic information is related to participants' age, gender, ethnicity, undergraduate program and year of study, and years of sport participation. PL is both an antecedent and consequence of physical activity (Edwards et al. 2017) and represents the lived experience of the PL journey of an individual (Sum et al. 2018a). A primary outcome measure was the participants' self-reported and objective physical activity levels. As there may be an over-reporting of the self-report physical activity levels, a subsample of 64 randomly selected student participants per intervention group also collected objective physical activity levels using accelerometers. Accelerometers were worn for at least 8 h per day in seven consecutive days during the first week of the semester. During the intervention, all lessons were videotaped and coded using the System for Observing Fitness Instruction (SOFIT) which elicits percentage of PE time at different intensities of physical activity, lesson context, and teacher involvement in PE lessons. Participants recompleted the questionnaire, and the subsample wore the accelerometers during the post-intervention phase (the 10th lesson at 11th week of semester) and the follow-up phase (15th week of semester).

Physical activity measures The globally standardized and validated short version of the International Physical Activity Questionnaire was used to measure self-report physical activity levels (Craig et al. 2003; Hallal et al. 2012). Four generic items of vigorous, moderate, walking, and sitting were included to obtain the physical activity levels from the participants. Example item included the following: During the last 7 days, on how many days did you do vigorous physical activity like heavy lifting, digging, aerobics, or fast cycling (vigorous)? The total

duration of different intensities of physical activity which occurred for at least 10 uninterrupted minutes in the last 7 days was used for calculations (Booth 2000).

Accelerometers (Actigraph wGT3X+) were used to measure the objective physical activity levels (light, moderate, and vigorous) of participants, and physical activity intensity was calculated as a metabolic value (Evenson et al. 2008). The dynamic range of accelerometers is \pm 6MET with 3 axes and 3 mg/LSB of sensitivity. Only data that recorded more than 8 h per day and 5 days per week were used for analysis.

SOFIT is a validated and reliable momentary time sampling and interval observation instrument to gather quantitative data for assessing physical activity during PE lessons (McKenzie et al. 1992). SOFIT includes three intensities of students' physical activity levels (lying down, sitting, standing, walking, vigorous), lesson context (general, knowledge, fitness, skill practice, game play, free time), and teacher behavior (promotes fitness, demonstrates fitness, instructs generally, manages, observes, or other task) or teacher interactions (promoting "in-class" or "out-of-class" physical activity). Each category is coded using interval coding every 20 s (10 s observe; 10 s record) throughout the lesson. The observer decides on what is occurring at the moment an observation interval ends.

Situational motivation scale (SIMS) The SIMS is a 16-item instrument that was used to measure participants' situational intrinsic and extrinsic motivation while performing given physical activities. The four behavioral subscales include intrinsic motivation, identified regulation, external regulation, and amotivation (Deci et al. 1991). Participants responded to the instrument on a 7-point Likert scale (1 = not at all true and 7 = very true). Example items include the following: (a) this activity is fun (intrinsic motivation); (b) I believe this activity is important for me (identified regulation); (c) I do not have any choice (external regulation); and (d) I do this activity, but I am not sure it is a good thing to pursue it (amotivation). Guay et al. (2000) reported adequate internal consistency ($\alpha = 0.77$ – 0.95) and construct validity in physical activity settings among college-aged students.

Physical activity enjoyment scale (PACES) PACES is a survey instrument that measures how much a student enjoys participating in physical activity. Participants responded to the 16-item instrument on a 5-point Likert scale (1 = disagree a lot and 5 = agree a lot). There are nine positive items such as "I find it pleasurable" and "It gives me energy" and seven negative items such as "I dislike it" and "It is not fun at all." Participants who receive high scores on positive items and low scores on negative items would indicate a high enjoyment of the physical activity. Motl et al. (2001) established adequate internal consistency ($\alpha = 0.81$ – 0.86) and factorial and construct validity of PACES with college-aged students.

Perceived physical literacy instrument (PPLI) The PPLI is a 9-item instrument that has been used to measure the perceived PL of teachers (Sum et al. 2016; Sum et al. 2018b), adolescents (Choi et al. 2018; Sum et al. 2018a), and coaches (Li et al. 2019). Three subscales within the instrument assess the PL attributes of "sense of self and self-confidence," "self-expression and communication with others," and "knowledge and understanding" (Whitehead 2010). Participants responded to the instrument on a 1 to 5 Likert scale (1 = strongly disagree and 5 = strongly agree). Example statements include the following: (a) I am physically fit, in accordance with my age (sense of self and self-confidence); (b) I have strong social skills (self-expression and communication with others); and (c) I am aware of the benefits of sports-related to health (knowledge and understanding). The scale scores are reliable with the internal consistency from 0.73 to 0.76 (Sum et al. 2016).

Empowering and disempowering motivational climate questionnaire in PE

(EDMCQ-PE) The EDMCQ-PE is a 34-item instrument based on achievement goal theory and self-determination theory to assess students' perceptions of empowering and disempowering features of the motivational climate created by their PE teachers. Participants responded to the instrument on a 1 to 5 Likert scale (1 = strongly disagree and 5 = strongly agree). Example statements include the following: (a) My teacher gave pupils choices and options (empowering) and (b) My teacher tried to interfere in aspects of pupils' lives outside of PE (disempowering). Milton et al. (2018) provided evidence of the EDMC-Q as internally consistent ($\alpha = 0.82-0.91$) and has factorial and construct validity.

Pilot study

A pilot study was conducted to ensure that the randomized controlled trial was scientifically valid (Lancaster et al. 2004). A convenience sample of 55 full-time undergraduate students was recruited to obtain their feedback on the data collection procedure and the comprehension of the questionnaire. Participants' ethnicity, studying program, and the year of study were added into the revised questionnaire which was also reviewed and considered to be content valid by experts in this area of research.

References

- Booth, M. (2000). Assessment of physical activity: An international perspective. *Research Quarterly for Exercise and Sport*, 71(2), 114–120.

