**Title: Effect of Sport Education in University Required PE on Students'
Perceived Physical Literacy and Physical Activity Level**

NCT number: NCT03888885

Date: 12/9/2021

Statistical Analysis Plan

ActiLife 6 software (ActiGraph LLC), a designated software for transferring data from accelerometers to computers, was used to transfer physical activity data with a metabolic cut point of Freedson et al. (1998). IBM SPSS statistics version 22 for Windows (IBM SPSS) was used for all data analysis (Field 2009). One-way analyses of variance (ANOVAs) were used to assess differences between groups in the baseline measures of demographic information, each outcome measure, as well as the mean percentage of physical activity levels, lesson context, and teacher involvement during PE lessons. Pearson's correlation was used to compute the association between self-report and objective physical activity levels. To evaluate the effect of the different types of curriculum interventions on outcome measures, a series of repeated-measures multivariate analysis of variance (MANOVAs) were used with time (baseline, post-intervention, and follow-up) as the within-subjects factor and group (intervention group and control group) as the between-subjects factors. MANOVA analyses are the most appropriate analyses to discern differences between groups over time and to establish any potential group by time interaction effects (Tabachnick and Fidell 2014). Specifically, MANOVA is likely to prevent type I error when dependent outcomes may be correlated and thus potentially share some of the same variances. Post hoc Scheffe analyses were conducted to determine contributing factors to significant MANOVA F values. The significance level was set at 95% for all analyses.

References

Field, A. (2009). *Discovering statistics using SPSS*. London: SAGE Publications Ltd.

Freedson, P. S., Melanson, E., & Sirard, J. (1998). Calibration of the computer science and applications, inc. accelerometer. *Medicine and Science in Sports and Exercise*, 30(5), 777–781.

Tabachnick, B. G., & Fidell, L. S. (2014). *Using multivariate statistics*. Harlow: Pearson Education Limited.

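### The power of 0.95 from 341 students is stated without condition although classes are randomised and no ICC, test or effect-size metric is given, and the 64-per-arm accelerometer part of the primary outcome has no stated power

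*Protocol*

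**What the plan says.** The protocol, under Eligibility and randomization, randomises classes, not students. It says "PE classes were initially grouped by lecturers and types of sports" before a computer-generated sequence assigned them to the two arms.

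On size, it says that "The required sample size of students was calculated based on the hypothesized effect sizes and the likely rates of participants dropout for outcome measures". It then gives "an estimated required cluster sample size of 341 with an effect size of 0.25, α of 0.05, and a power of 0.95". After an allowance for 10–20% dropout, "this led to a required number of 8 classes for each of the sport education and traditional groups", which is 16 classes in all.

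Under Data collection protocol, a primary outcome measure is the students' "self-reported and objective physical activity levels". The objective part comes from "a subsample of 64 randomly selected student participants per intervention group". Under Physical activity measures, a wear-time rule applies: "Only data that recorded more than 8 h per day and 5 days per week were used for analysis".

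The SAP plans repeated-measures MANOVAs "with time (baseline, post-intervention, and follow-up) as the within-subjects factor and group (intervention group and control group) as the between-subjects factors". It contains no power statement and no ICC.

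**The concern.** When whole classes are randomised, students in one class tend to resemble each other, and the information in 341 students is less than that in 341 independent ones. A power figure for such a design needs an ICC, a class size and degrees of freedom based on the number of classes. None is shown. The word cluster before the sample size is the only sign of an allowance, and a label cannot be checked. The test, its df and the meaning of 0.25 are also missing, so a reader cannot rebuild 341 or 0.95.

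The accelerometer subsample is a second gap. It exists because self-report may overstate activity, it supplies the objective half of a primary outcome measure, and no effect size, power or loss allowance is attached to it.

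What is at stake is how a null result on physical activity would be read. An unconditional 0.95 invites the conclusion that an effect of the stated size has been ruled out, and the documents do not secure that.

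**Working it through.** **Inputs from the protocol.** N = 341; effect size 0.25; alpha 0.05; power 0.95; 16 classes; dropout 10–20%; 64 accelerometer students per arm.

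**Assumptions, because the documents are silent.** Two-sided test; ICC from 0.01 to 0.10; equal classes, so m = 341/16 = 21.3 (actual class sizes may be in the figure or table not shown); one outcome at one time point; no baseline adjustment; no effect of the lecturer and sport grouping on variance or df.

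**Step 1: can 341 be reproduced?** Not for a two-arm comparison.
- 0.25 as f (equal to d = 0.5 with two groups): an F test with 1 numerator df needs 210 in total.
- 0.25 as d: 2 × (1.960 + 1.645)² / 0.25² ≈ 416 per arm, 832 in total.
- An F test with f = 0.25 and 6 numerator df (for example seven groups) first reaches 0.95 at exactly 341 (power 0.951), with no design effect. The documents state no such test.
- A hidden allowance is also possible: 341/210 = 1.62, and (1.62 − 1)/(21.3 − 1) gives an ICC of about 0.03.

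The last two routes fit 341 but contradict each other on whether clustering was allowed for.

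**Step 2: from 341 to 16 classes.** 341/0.9 = 379 and 341/0.8 = 427 students, or about 24 to 27 per class. Dropout is the only reason given for this step.

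**Step 3: power of 16 classes, 341 analysed.** Design effect DE = 1 + (m − 1) × ICC; effective n per arm = 170.5/DE; noncentrality = d × √(n/2); noncentral t on 16 − 2 = 14 df; d = 0.5.

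| Assumed ICC | DE | Effective n per arm | Noncentrality | Power |
|---|---|---|---|---|
| 0.01 | 1.20 | 141.7 | 4.21 | 0.97 |
| 0.02 | 1.41 | 121.2 | 3.89 | 0.95 |
| 0.05 | 2.02 | 84.6 | 3.25 | 0.86 |
| 0.10 | 3.03 | 56.3 | 2.65 | 0.69 |

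On these assumptions 0.95 holds up to an ICC of about 0.02. If 0.25 is d, power is 0.63 with 341 independent students (339 df), and 0.50, 0.44, 0.33 and 0.24 at the four ICCs.

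**Step 4: accelerometer part, d = 0.5, one time point.**
- Independent students: 0.80 with 64 per arm (126 df). After 20% loss, 64 × 0.8 ≈ 51 per arm: 0.71.
- ICC 0.05, 14 df, 128/16 = 8 per class: DE = 1 + 7 × 0.05 = 1.35, effective n = 64/1.35 = 47.4, power 0.62.
- The same after 20% loss, 102/16 = 6.4 per class: DE = 1.27, effective n = 40.2, power 0.55.
- Power of 0.95 with 64 independent students per arm needs d of about 0.64.

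**Step 5: does repeated measurement rescue the figure?** It depends on the within-person correlation r, which is not stated. For a baseline-to-post change, with r the same at class and student level, the variance is multiplied by 2(1 − r). At ICC 0.05 and N = 341, power is then 0.72 at r = 0.3, unchanged at 0.86 at r = 0.5, and 0.97 at r = 0.7.

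**The case against.** The strongest reply is that nothing here shows 0.95 to be wrong. If 0.25 is f and the ICC is 0.02 or less, 16 classes deliver it, and no passage places the ICC higher. A strong within-person correlation would carry 0.95 to larger ICCs, and the label on 341 may reflect a real allowance. All of this stands. A reader might infer that the trial was underpowered, or that clustering was ignored when 341 was derived; the documents support neither. What remains is that the figure is given without the conditions on which it depends.

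On the accelerometers, the subsample serves partly to check self-report, and the SAP plans a correlation between the two measures. The protocol attaches 0.95 to 341 and never to the 64, so a reader who carries it across makes an inference that the text does not make. But objective activity is named within a primary outcome measure, so asking for its power is fair.

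The missing figure and table may hold class sizes, but the text cites them for allocation, lecturers and courses, not for power inputs.

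The SAP's MANOVA names only time and group as factors. Leaving class out of that model mainly threatens the type I error rate. That is a separate matter and is not counted here.

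**Conclusion.** The point holds as an unsupported power figure on a primary outcome, not as proven underpowering. That no ICC, design effect, test or metric is given, and that no power is stated for the 64 per arm, follows directly from the documents. So does the failure of the stated inputs to yield 341 for two arms under either reading of 0.25.

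The sizes are conditional. The range of 0.97 to 0.69 rests on assumed ICCs of 0.01 to 0.10, equal classes, d = 0.5, a single time point and 14 df. It could move either way with repeated measures or with the grouping by lecturer and sport. The metric matters at least as much as the ICC: reading 0.25 as d lowers power to about 0.63 before any clustering. The accelerometer result needs no ICC: at d = 0.5 and one time point, 64 per arm gives about 0.80 at best, before dropout and wear-time exclusion.

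**What to change.** Keep 341 as the recruitment basis and state the test, degrees of freedom and effect-size metric from which it came, including any design effect that was used. Replace the unconditional 0.95 with the power that 16 classes give over a stated range of ICCs, from an analysis that accounts for class and with df that reflect the grouping by lecturer and sport. If repeated measures are credited, state the within-person correlation and the assumed course of the effect over the three time points; if these are not known, show a range.

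State accelerometer power separately on the same basis, after expected loss and wear-time exclusion.

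No extra enrolment is needed for this disclosure. The sponsor must commit to an assumed ICC range, and the stated power will look less favourable over much of it. The power must also refer to an analysis that accounts for class, which the SAP's MANOVA as written does not.

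### The only stated accelerometer wear requirement is the same 8 h figure as the analysis cut-off, so the objective activity measure has no margin in hours and may miss much of the waking day

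*Protocol*

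**What the plan says.** Protocol, Data collection protocol, gives the baseline wear, in the semester's first week: "Accelerometers were worn for at least 8 h per day in seven consecutive days". The device is used in a subset only: "a subsample of 64 randomly selected student participants per intervention group also collected objective physical activity levels using accelerometers". Wear is repeated twice: "the subsample wore the accelerometers during the post-intervention phase (the 10th lesson at 11th week of semester) and the follow-up phase". No hour figure is restated for those two later waves.

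Protocol, Physical activity measures, gives the rule for keeping data: "Only data that recorded more than 8 h per day and 5 days per week were used for analysis".

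The Data collection protocol section names self-reported and objective activity together as a primary outcome, and justifies the accelerometer by possible over-reporting on the questionnaire. The questionnaire asks about the last 7 days. The SAP correlates the self-reported and objective levels, and analyses outcomes "with time (baseline, post-intervention, and follow-up) as the within-subjects factor".

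The allowance for loss under Eligibility and randomization ("In anticipation of 10–20% of the dropout rate across data collection phases") leads to the number of classes. No allowance is stated for the 64 per group.

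**The concern.** A wear requirement normally sits well above the validity minimum, so that a somewhat short day still counts. Here both are 8 h. A day that misses the requirement by a few minutes is lost, and nothing in hours absorbs the shortfall.

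The second issue is coverage. The outcome is the student's activity level, but an 8 h floor is satisfied by wearing the device for only part of the waking day. Activity outside the worn hours is not recorded, while the questionnaire it is compared with covers the whole week.

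At stake are the number of usable students in a subsample of 64 per group measured at three waves, and how well the recorded hours represent habitual activity.

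**Working it through.** **Inputs from the documents.** Wear floor: 8 h on 7 days. Validity: more than 8 h on 5 days. Subsample: 64 per group. Waves: 3. The documents give no effect size, power or attrition for the 64, so that figure cannot be reproduced. They also give no wear-time distribution or wear-time algorithm. Every wear pattern below is an assumption.

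**1. The two rules side by side.**

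| | Wear | Kept for analysis |
|---|---|---|
| Hours per day | 8 or more | above 8 |
| Days | 7 | 5 |

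Margin in hours: 8 − 8 = 0. Margin in days: 7 − 5 = 2. If *more than* is read as also governing the 5 days, six days are needed and the margin is 1.

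**2. Effect of the inequality alone.** It removes a student who met the floor every day only if at least 3 of 7 days record exactly 8 h (at least 2 of 7 on the stricter reading). With daily wear normal (mean μ, SD σ, in minutes) and recorded in whole minutes:

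- p(at least 8 h) = 1 − Φ((479.5 − μ)/σ)
- p(more than 8 h) = 1 − Φ((480.5 − μ)/σ)
- P(valid week) = Σ C(7,k) pᵏ(1 − p)⁷⁻ᵏ for k = 5 to 7

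For μ = 480, σ = 60, p is 0.5033 against 0.4967 and P(valid week) is 0.2321 against 0.2211. The difference is 0.0109, and 64 × 0.0109 = 0.70 students per wave.

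| μ, σ (min) | Students of 64 lost per wave |
|---|---|
| 480, 60 | 0.70 |
| 540, 90 | 0.47 |
| 600, 120 | 0.17 |
| 720, 120 | 0.001 |
| 480, 30 (extreme) | 1.4 |
| 480, 15 (extreme) | 2.8 |

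If wear is recorded to the second, the loss is below 0.05 in every row. For scale, if d = 0.5 is assumed and clustering ignored, a two-sided t-test at α = 0.05 has power 0.801 with 64 per group and 0.795 with 63.

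**3. Coverage.** With an assumed 16 h waking day, the floor covers 8/16 = 50%.

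**4. How the valid-week rate depends on mean wear (illustration).** Let daily wear be normal with SD 2.5 h, so p = Φ((mean − 8)/2.5). Mean 9 h gives Φ(0.4) = 0.655. Mean 12 h gives Φ(1.6) = 0.945. Days within a student are correlated, so use a beta-binomial with a = p(1 − ρ)/ρ and b = (1 − p)(1 − ρ)/ρ, and take P(at least 5 of 7).

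| Mean wear | ρ | a, b | P(valid week) | Of 64 |
|---|---|---|---|---|
| 9 h | 0.2 | 2.62, 1.38 | 0.562 | 36 |
| 9 h | 0.4 | 0.98, 0.52 | 0.582 | 37 |
| 12 h | 0.2 | 3.78, 0.22 | 0.957 | 61 |
| 12 h | 0.4 | 1.42, 0.08 | 0.941 | 60 |

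The two spare days are already counted here.

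**The case against.** A reader might infer that students who do just what is asked are excluded, and that the 64 per group shrinks as a result. The documents do not support that. The 8 h is a floor, so longer wear also complies, and two of the seven days may fail. A student who meets the floor every day is lost only by recording exactly 8 h on several days, which step 2 shows to be negligible.

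A reader might also take the valid-week rates in step 4 as losses caused by the matching figures. They are not. Days under 8 h breach the wear floor as well as the analysis rule, and they would be invalid under either inequality. The contrast between 9 h and 12 h shows how sensitive the rule is to mean wear. It does not estimate what a reworded request would achieve, and nothing in the documents supports either mean.

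The protocol sentence describes wear and does not reproduce the instruction given to students. They may have been asked to wear the device all day. A minimum does not fix actual wear, so the half-day gap is what the stated requirement permits and not what is known to have happened.

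All of this stands and limits the size of the point. It does not remove the lack of a margin in hours, or the absence of any stated wear target above the cut-off.

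**Conclusion.** The point holds as a minor one. The only wear requirement in the documents equals the analysis cut-off in hours, with two spare days as the sole buffer, and it permits about half of an assumed 16 h waking day to go unmeasured on an objective measure that belongs to a primary outcome.

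The differing inequalities should be reconciled for consistency, but they cost under about 1 of 64 students per wave in plausible cases. How many students are lost to days under 8 h cannot be determined from the documents. The 56–58% and 94–96% figures rest on assumed means, an assumed SD of 2.5 h and an assumed within-student correlation of 0.2 to 0.4. Whether a new instruction would move mean wear between those values is a further assumption.

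**What to change.** In the Data collection protocol section, ask the subsample to wear the device during all waking hours on all seven days, and state this for baseline, post-intervention and follow-up alike. Keep 8 h on at least 5 days as the minimum for a valid week, and write it as *at least 8 h* and *at least 5 days* wherever the rule appears.

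The cost is a changed wear instruction and a few words of protocol text, with no extra devices or staff. The downside is slightly more burden for 2 × 64 = 128 students. The protocol is written in the past tense; where wear has already been collected, only the wording of the validity rule can still be changed, and the wear request applies to future use of the design.
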